12.3.2 Dose Reduction

Any AE of \geq Grade 3 and attributed as possibly, probably or definitely related to sirolimus will result in the dose being held until the AE has resolved to \leq grade 1 or baseline. If the AE resolves, reinstitution of treatment can occur but at a reduced dose of 1mg daily. If the AE recurs at the reduced dose, treatment will be held and the subject will be withdrawn from the study. Of note, an escalation in patient's level of care (e.g. floor to ICU) or the need for advanced respiratory support will not automatically result in dose reduction of the study drug, unless deemed necessary for patient safety by the PI or the treating clinicians feel it is in the patient's best interest to be withdrawn \pm unblinded. In case the dose of study drug is altered in a subject, in order to maintain blind, a corresponding change will also be made in a placebo subject. Toxicities that may be attributable to sirolimus are listed in Sections 9.1 and 14.3.6. If

any of these AEs occur at grade ≤ 2 , sirolimus may be continued and the AE managed with supportive care. For any AE with a grade ≥ 3 , the rules outlined in Sections 14.2 – 14.10 apply for holding of dose, dose reduction, removal from study and reporting requirements.

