4.1 Main Study Objective

The main objective of our study is to determine if treatment with sirolimus can improve clinical outcomes in hospitalized patients with COVID-19.

4.2 Primary Endpoint:

Progression to respiratory failure requiring advanced support measures, either due to inadequate ventilation (non-invasive or invasive mechanical ventilation) or inadequate oxygenation (CPAP* or high flow supplemental oxygen at rates \geq 15 liters/minute), in patients given sirolimus compared to the placebo group.

4.3 Secondary Endpoints:

Key secondary endpoints:

- Escalation in level of care
- Increase in total lymphocyte count
- Normalization of biomarkers (Ferritin, LDH, and d-dimer)
- Survival to hospital discharge
- Drug safety profile (Incidence and type of adverse and serious adverse events)

Other outcomes measures:

- Fever
- Duration of advanced respiratory support
- Duration of hospital stay (in survivors)
- Time from treatment initiation to death (in non-survivors)
- Need for initiation of other off-label rescue therapies such as Anti IL-6 agents, at the discretion of treating clinicians

* CPAP use for known obstructive sleep apnea will not be considered as disease progression.

5. Study Design

We will employ a randomized, double blind, placebo-controlled study design. 30 patients hospitalized with COVID-19 and meeting the inclusion criteria specified below will be randomized to receive sirolimus or placebo in a 2:1 manner. The treatment regimen and duration are provided in Sections 5.5 and 5.6.

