5.5 Study Drug Treatment

Patients who meet eligibility criteria, provide informed consent and are enrolled in the study will be randomized to receive sirolimus or placebo in a double-blind manner and a 2:1 randomization scheme in favor of sirolimus. The sirolimus dose for the study will be 6mg daily on day 1 followed by 2mg daily for a maximum treatment duration of 14 days, or until hospital discharge, whatever happens first. The study drug will be provided by the drug manufacturer, Pfizer, encapsulated and dispensed by the University of Cincinnati's Investigational Drug Services (IDS) Pharmacy, and given to the patients by their bedside nurse. Patients will be reminded about the side effects of sirolimus. Every attempt will be made to give the medication at the same time every day. Chart reviews will be conducted on a daily basis to determine changes in clinical status, concomitant medications and laboratory parameters. Study specific biomarkers will be measured at baseline and then at days 3, 7 and 14. Section 6.2 provides a detailed description of the study specific schedule of events. Patients will be instructed to

contact the study staff should they experience any side effects. Study drug may be held or reduced in the event of unacceptable side effects.

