7.1 Participant withdrawal criteria

Participants may be terminated early from the study for the following reasons:

- a. The participant elects to withdraw consent from study activities.
- b. The participant dies.
- c. The participant has a serious allergic or anaphylactic reaction to the study drug
- d. The participant's condition deteriorates significantly necessitating either a transfer to the intensive care unit (ICU) or the need for advanced respiratory support (high flow oxygen ≥ 15 L/minute, CPAP, non-invasive or invasive mechanical ventilation), and the treating clinician thinks it is in the best interest of the patient to be withdrawn \pm unblinded. If the patient is unblinded, any open label use of sirolimus after that will be based on clinical grounds at the discretion of the treating clinician(s). The study drug (sirolimus or placebo) will continue for the maximum stipulated duration of 14 days regardless of escalation in care, unless the patient is withdrawn from the study.
- e. In the opinion of the investigator, it is not in the participant's best medical interest to continue to participate in the study.

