11.4 Assessment of compliance with the investigational product

Assessment of compliance will be done by daily review of the medication administration record (MAR) in the study subject's medical chart. In case of lack of absolute clarity regarding study drug administration based on MAR review, contact will be made with one or all of the following: patient's bedside nurse, investigational pharmacy, and the study subject, in order to determine if the daily dose of the study drug was administered.

12. Modification or discontinuation of the investigational product

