14.7 Definition of Attribution

The attribution of an AE to the study drug will be determined by the PI or designated physician co/sub-investigator. The PI or designee will record the determination of attribution on the

appropriate AE or SAE form. The attribution of an AE to the investigational drug or to a study procedure will be determined using the descriptors in the following table. For the purpose of this study, in addition to all study medications, the following procedures will be considered when determining attribution:

Code	Descriptor	Definition (guidelines)
UNRELATED CATEGORY		
1	Unrelated	The adverse event is clearly not related to study. The event is completely related to an etiology other than the study product or study intervention (the alternative etiology must be documented in the study subject's medical record)
2	Unlikely	The adverse event is doubtfully related to study and likely to be related to factors other than study product or study intervention.
RELATED CATEGORIES		
3	Possible	The adverse event may be related to study. There is an association between the event and the administration of study product and there is a plausible mechanism for the event to be related to the study product; there may be also an alternative etiology, such as characteristics of the subject's clinical status and/or underlying disease
4	Probable	The adverse event is likely related to study. There is (1) an association between the event and the administration of study product or study intervention, (2) a plausible mechanism for the event to be related to the study product, and (3) the event could not be reasonably explained by known characteristics of the subject's clinical status and or an alternative etiology is not apparent
5	Definite	The adverse event is clearly related to study. There is (1) an association between the event and the administration of the study product or study intervention, (2) a plausible mechanism for the event to be related to the related to the study product, and (3) causes other than the study product have been ruled out and/or the event re-appeared on re-exposure to the study product

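### Section 12.3.2's matched dose change, read literally, can mark a second subject as placebo and does little to protect the blind

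*Combined protocol and SAP*

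**What the plan says.** Section 5 of the protocol sets the design: "We will employ a randomized, double blind, placebo-controlled study design". Thirty subjects are allocated 2:1, so 20 to sirolimus and 10 to placebo.

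Section 12.3.2 ties holds and reductions to a clinical event. An adverse event of grade 3 or higher "attributed as possibly, probably or definitely related to sirolimus will result in the dose being held". It then adds a blinding rule, set off by a change to any one person's study drug: "in order to maintain blind, a corresponding change will also be made in a placebo subject". Section 7.1 makes clear that study drug covers both arms: "The study drug (sirolimus or placebo) will continue for the maximum stipulated duration of 14 days".

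Section 14.7 says who judges relatedness: "The attribution of an AE to the study drug will be determined by the PI or designated physician" or sub-investigator. Under Section 5.5 the doses are "given to the patients by their bedside nurse", and under Section 11.4 study staff check the medication administration record every day. Sections 11.1 and 12.1 provide over-encapsulated tablets, lactose placebo capsules and a matching liquid placebo.

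No other section withdraws or limits the matched-change rule. The SAP covers only sample size and analysis and does not mention it.

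**The concern.** A matched sham change protects a blind when the trigger is hidden and occurs in one arm only, such as an adjustment made on a drug level. Nothing of that kind is planned here: neither the schedule in Section 6.2 nor the laboratory list in Section 8.3 includes a sirolimus level. The trigger is an adverse event that staff can see, that can occur in either arm, and that can be graded and attributed without knowing the allocation. With matched product, a change made for a subject's own event gives little away.

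The linked change in a second subject does carry information, because only placebo subjects are eligible for it. It also requires an unblinded person to choose the subject.

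The stake is the primary endpoint. Starting oxygen at 15 L/min or more, CPAP or non-invasive ventilation is a bedside decision. So are rescue therapy (Section 4.3) and withdrawal with or without unblinding (Section 7.1). If the treating team can guess that a patient is on placebo before making those decisions, they are no longer fully masked. The direction of any resulting bias cannot be settled from the documents.

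**Working it through.** The plan states no figure on this point, so there is nothing to reproduce. The check is what an observer learns from a dose change that has no visible cause.

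**Inputs.** N = 30 at 2:1 (Section 5), so 20 sirolimus, 10 placebo, and prior P(placebo) = 10/30 = 1/3. The matched change goes only to a placebo subject (Section 12.3.2, literal reading).

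**Step 1: the second subject.** Let *m* be the chance that a placebo subject receives a visible matched change. Let *b* be the chance, equal in both arms, of a change that looks unexplained for some other reason. Then

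P(placebo | unexplained change) = (1/3)(m + b) / [(1/3)(m + b) + (2/3)b] = (m + b) / (m + 3b).

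- No matched changes (m = 0): b/3b = 1/3, so nothing is learned.
- No other unexplained changes (b = 0): m/m = 1.
- Equal rates (m = b, hypothetical): 2/4 = 0.50.
- Matched changes four times as common (m = 4b, hypothetical): 5/7 = 0.71.

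The documents give neither *m* nor *b*. The result is therefore a rise from 1/3 towards 1, not a fixed value.

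**Step 2: comparison with a pick that ignores arm.** If the second subject were drawn from the other 29 without regard to arm, P(placebo) would be 10/29 = 0.34 when the first subject is on sirolimus and 9/29 = 0.31 when the first is on placebo. Both are close to 1/3. The information comes from choosing the subject because of the arm.

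**Step 3: the first subject.** If a match is made only when a sirolimus subject is changed, seeing the match raises the first subject's probability of sirolimus from 2/3 to 1. If either arm sets it off, at equal rates, that probability stays at 2/3. The wording refers to study drug in a subject, which fits either arm, but the sentence does not say so outright.

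**Step 4: visibility.** A held dose shows at the bedside (Section 5.5) and in the daily record review (Section 11.4). The physician who attributes events (Section 14.7) knows who had no qualifying event. A silent swap of capsule contents would not be seen, but it would then mask nothing.

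**Step 5: size per event.** Each visible matched change exposes 1/10 = 10% of the placebo arm, or 1/30 = 3.3% of the trial.

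**Step 6: why one subject matters.** The plan calls the difference clinically meaningful if its 80% interval excludes zero. It names no interval method; a Wald interval is assumed here (z = 1.2816).

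- 5/10 v 5/20 (the planning rates): SE = √(0.25/10 + 0.1875/20) = 0.1854, interval 0.25 ± 0.238 = 0.012 to 0.488.
- 4/10 v 5/20: SE = √(0.24/10 + 0.1875/20) = 0.1827, interval 0.15 ± 0.234 = −0.084 to 0.384.

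Reclassifying one placebo subject changes the conclusion in this example. This shows sensitivity only; it does not estimate bias.

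**The case against.** The strongest reply is that the sentence is only badly worded. The rules around it are written in terms of sirolimus, and this is the one sentence in Section 12.3.2 that extends dose changes to placebo. The authors may have meant that placebo subjects with their own adverse event are handled in the same way. That is possible, but the text does not say it. A change in one subject that is also made in a placebo subject more naturally describes two people. If equal handling was the intent, the sentence still needs the same correction.

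A reader might infer that the rule unmasks placebo subjects with certainty. The documents do not support that. Section 12.3.1 allows interruptions for procedures and delays for non-treatment-related grade 3 and 4 events, and Sections 7.1 and 12.3.2 allow for clinician judgement, so a hold can have other explanations. Nothing shows that nurses or treating clinicians know this rule or the attribution decisions. A reduction inside an identical capsule need not be seen. This objection stands, and it is why the working gives a range.

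A reader might also put a figure on it: if 10% to 20% of 20 sirolimus subjects were altered, 2 to 4 of the 10 placebo subjects would be exposed. No section gives such a rate. The calculation also needs a different placebo subject, on treatment at the time, for every match. Section 12.3.1 itself expects interruption for toxicity to end mostly in withdrawal. The figure should not be used.

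Finally, the Investigational Drug Services pharmacy dispenses the drug (Section 5.5) and keeps participant-level records (Section 11.3), so it could plausibly carry out the match. That is fair. The remaining gap is that nobody is named. The only unblinded role described is the DSMB's safety review (Section 14.1), and the protocol does not say what happens if no placebo subject is on treatment.

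**Conclusion.** The point holds in a limited form. Followed literally, a rule meant to maintain the blind can weaken it for the second subject and adds little masking for the first. The probability that the second subject is on placebo rises from 1/3 towards 1 for an observer who knows the rule, sees the change and sees no other reason for it.

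The total effect cannot be estimated, because the documents give no rate of dose changes. Per event, one of 10 placebo subjects is exposed. A reader might infer that the primary result would be biased; that goes further than the documents allow. Only a matched change made before that subject progresses could influence the endpoint, and the plan expects half the placebo arm to progress, with study drug allowed to continue afterwards. The conclusion rests on the literal reading of one sentence and on a hold being visible in the record or at the bedside.

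**What to change.** Reconcile the matched-change sentence in Section 12.3.2 with the double-blind design in Section 5. The revised text should make three things clear:

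- Any change in study drug follows from that subject's own course under the protocol's existing rules, applied by blinded staff regardless of arm.
- The investigational pharmacy supplies matched product for any change and is named as the party holding allocation for this purpose.
- No change is made in another subject because that subject is known to be on placebo.

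This proposes and alters no dose, threshold or hold rule. The cost is one sentence and one pharmacy instruction, and it removes a procedure from the trial. If the authors meant equal handling of placebo subjects with their own adverse events, the same edit says so.

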12.3.3 Concomitant medications

All concomitant medications including taken during the course of the study will be documented on a CRF on a daily basis. This record will include start and stop dates, dose, and indication for use for each concomitant medication.

12.3.4 Prohibited medications

Metabolism of sirolimus occurs in the liver and the small intestine by the CYP3A4 family of enzymes. Thus, concomitant administration of sirolimus with other CYP3A substrates or inducers can alter the oral bioavailability of sirolimus.³³ Because of the potential interaction with other drugs involving CYP3A4 metabolic pathways, strong inhibitors and strong inducers of CYP3A4 will not be allowed to be used concomitantly with the study medication. Similarly, patients on chronic immunosuppressive medications may be at higher risk of adverse effects from sirolimus and will be excluded from study participation. A list of the prohibited medications is provided below. While this list covers the majority of medications, the PI will carefully review the concomitant medications in each potential subject prior to enrollment to ensure the study drug can be given safely. In case, a subject is not enrolled due to a concomitant medication not listed in this table, we will note medication and the rationale on our screening log.

List of prohibited medications for this study	
Strong CYP inducers	
Barbiturates	
Carbamazepine	
Phenytoin	
Rifampin, Rifabutin	
St. John's Wort	
Strong CYP inhibitors	
Ketoconazole	
Voriconazole	
Itraconazole	
Nefazodone	
Clarithromycin	
Erythromycin	
Telithromycin	
Gemfibrozil	
Grapefruit juice	
Chronic immunosuppressive medications	
TNF inhibitors such as infliximab, adalimumab, and etanercept	
Methotrexate	
Azathioprine	
Leflunomide	
Cyclosporine	
Cyclophosphamide	
Rituximab	
Chronic prednisone ≥ 20 mg daily	
Mycophenolate mofetil	

13. Procedures

13.1 Stopping rules

13.1.1 Study discontinuation

The DSMB and the IRB have the authority to stop or suspend this trial at any time. This study may be suspended or closed if:

- Early stopping rules have been met
- The study objectives have been met
- The study chair/investigators believe it is not safe for the study to continue
- The DSMB suspends or closes the trial

13.1.2 Subject discontinuation

An intent-to-treat approach will be used. All data acquired prior to termination for the reasons outlined below will be included in the primary analysis unless patient withdraws consent. Every effort will be made to conduct a final study visit with the participant and participants will be followed clinically until, if applicable, all AEs attributable to study drug resolve. Please refer to Section 7.1 for a list of the reasons that may lead to participant withdrawal from the study.

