6.2 Schedule of Events

Event	Screening ¹	D1	D2	D3	D4	D5	D6	D7	D8	D9	D10	D11	D12	D13	D14 ⁶	F/u ⁷
Informed consent	X															
Demographics	X															
Medical history	X															
Determine study eligibility	X															
Con meds	X	X	X	X	X	X	X	X	X	X	X	X	X	X	X	
Review AEs			X				X								X	
Heart rate/pulse ²	X	X	X	X	X	X	X	X	X	X	X	X	X	X	X	
MAP ²	X	X	X	X	X	X	X	X	X	X	X	X	X	X	X	
Highest daily temperature (F)	X	X	X	X	X	X	X	X	X	X	X	X	X	X	X	
Oxygen saturation ²	X	X	X	X	X	X	X	X	X	X	X	X	X	X	X	
FiO ₂ (%) ^{2, 3}	X	X	X	X	X	X	X	X	X	X	X	X	X	X	X	
Pregnancy test ⁴	X															
LDH ⁵	X			X				X							X	
Ferritin ⁵	X			X				X							X	
D-dimer ⁵	X			X				X							X	
Absolute lymphocytes ⁵	X			X				X							X	
CBC (WBCs, Hb, Platelets) ⁵	X			X				X							X	
Serum creatinine ⁵	X			X				X							X	
AST, ALT ⁵	X			X				X							X	
Advanced resp. support (Y/N)	X	X	X	X	X	X	X	X	X	X	X	X	X	X	X	
Vital status	X	X	X	X	X	X	X	X	X	X	X	X	X	X	X	

¹ Screening visit can be the initial visit if a patient meets all inclusion/exclusion criteria

² Mean recorded value for the 24-hour duration of that day

³ FiO₂ (%) will be recorded if directly available from chart review such as in patients on ultra-high flow devices (vapotherm, optiflow etc.) or in patients on advanced respiratory support. For all other patients, FiO₂ (%) will be calculated based on the following conversion:

Supplemental O ₂ (l/min)	0	1	2	3	4	5	6	7	8	9	10	11	12	13	14
FiO ₂ (%)	21	24	27	30	33	36	39	42	45	48	51	54	57	60	63

⁴ Only required for women of childbearing potential, if not already obtained clinically

⁵ No need to recheck if already drawn clinically in the 24 hours prior to the study-specified time. If not checked clinically, these can be measured as research tests. If COVID-19 biorepository sample obtained on the day of these tests, they can be postponed to the next day.

⁶ In case a patient is discharged from the hospital before the 14-day period, their last hospital day will be treated similar to Day 14 with regards to study assessments

⁷ Long term outcomes following the 14-day study period will be assessed by chart reviews

Abbreviations: AE = adverse event, ALT = Alanine aminotransferase, AST = Aspartate aminotransferase, CBC = complete blood count, F = degrees Fahrenheit, FiO₂ = Fraction of inspired oxygen, Hb = Hemoglobin, LDH = Lactate dehydrogenase, MAP = Mean arterial pressure, WBCs = White blood cells

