If the patient agrees, we will confirm that the patient has access to a copy of the ICF with them and proceed with the steps outlined above. Prior to obtaining signatures, we will explicitly solicit any questions from the subject and ensure that all questions have been answered to their satisfaction.

After obtaining informed consent, we will review the inclusion/exclusion criteria to determine study eligibility. For patients who provide informed consent and meet all eligibility criteria, the screening visit can be their initial study visit. We anticipate that in most patients the

screening visit will be the initial study visit, and the following additional steps will be completed during the visit:

- Review medical history
- Record current medications
- Record vital signs: heart rate, blood pressure, temperature as specified in Section 6.2
- Record baseline oxygenation indices: oxygen saturation and FiO_2 as specified in Section 6.2
- For women of childbearing potential, obtain a urine pregnancy test, if not already obtained during the hospitalization
- If not already obtained clinically in the previous 24 hours, then obtain measurements for study specific biomarkers: LDH, ferritin, d-dimer, and absolute lymphocyte count
- If not already obtained clinically in the previous 24 hours, then obtain other laboratory parameters: CBC (total WBCs, Hb, Platelets), serum creatinine, AST, and ALT

Subsequent visits

Subjects' medical chart will be reviewed on a daily basis after study enrollment. The following parameters will be obtained on a daily basis from chart review:

- Vital signs: heart rate, blood pressure, temperature as specified in Section 6.2
- Oxygenation indices: oxygen saturation and FiO_2 as specified in Section 6.2
- Concomitant medications
- Advanced respiratory support use status
- Vital status

In addition, the following activities will be performed on days 3, 7 and 14 of the study

- If not already obtained clinically in the previous 24 hours, then obtain measurements for study specific biomarkers: LDH, ferritin, d-dimer, and absolute lymphocyte count. If COVID-19 biorepository sample obtained on the day of these tests, they can be postponed to the next day.
- If not already obtained clinically in the previous 24 hours, then obtain other laboratory parameters: CBC (total WBCs, Hb, Platelets), serum creatinine, AST, and ALT

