12.3 Medication adjustments

12.3.1 Dose Delays

For patients who are unable to tolerate the protocol-specified dosing schedule, dose adjustments are permitted in order to keep the patient on study drug. If administration of sirolimus must be interrupted because of unacceptable toxicity, drug dosing will be interrupted or modified according to rules described in Section 12.3.2. Given the short trial duration, this will likely result in participant withdrawal from the study. Sirolimus therapy may also be interrupted to accommodate surgical procedures or other invasive therapies at the discretion of treating clinicians. Major Events are non-treatment-related grade 3 and 4 pulmonary and non-pulmonary toxicities. Treatment should be delayed for major events if sirolimus may further complicate the non-treatment related event. If a major event requires a delay of treatment, treatment must be delayed until toxicity is resolved (\leq Grade 1 or \leq Baseline). For treatment-related toxicities and major events, if toxicity is not resolved in \leq 4 weeks, patient will be taken off the treatment that is most likely to be related to the toxicity.

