13.1.4 Individual early stopping rules

A study participant will be terminated from the study if any of the following occurs during the study:

- Recurrent or persistent sirolimus-related toxicity unresponsive to treatment in spite of dose adjustments.
- Pregnancy
- The participant refuses to continue in the study
- The investigator determines that the participant should be withdrawn from the study for reasons not listed above

A subject will be considered evaluable if they took one dose of the study drug. Subjects who are withdrawn before initiating treatment will be considered as premature discontinuation, and will be replaced by another participant.

Every effort will be made to obtain endpoint evaluations for subjects who withdraw or who discontinue prematurely from the study. The same evaluations performed at final visit will be completed at the time of termination. If withdrawal is due to inability to tolerate investigational drug or other untoward event related to investigational drug, the withdrawal will be noted in data analysis as treatment failure.

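### The primary analysis is labelled intent-to-treat, but the withdrawal rules secure endpoint data only up to termination and leave an undefined treatment-failure label in the analysis

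*Combined protocol and SAP*

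**What the plan says.** Section 13.1.2, Section 15 and the SAP's Data Analysis Plan all adopt intent-to-treat for the primary outcome. Section 13.1.2 then states: "All data acquired prior to termination for the reasons outlined below will be included in the primary analysis unless patient withdraws consent".

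Section 13.1.4 contains three relevant statements:
- "Every effort will be made to obtain endpoint evaluations for subjects who withdraw or who discontinue prematurely from the study".
- The next sentence: "The same evaluations performed at final visit will be completed at the time of termination".
- For withdrawal because the drug was not tolerated, or because of another drug-related event: "the withdrawal will be noted in data analysis as treatment failure".

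Other sections bear on what happens after withdrawal:
- Section 6.3 says of enrolled subjects that their "medical chart will be reviewed on a daily basis after study enrollment". Section 8.5 lists advanced respiratory support and vital status among the chart-review items. Footnote 7 of Section 6.2 adds: "Long term outcomes following the 14-day study period will be assessed by chart reviews". None of these excludes withdrawn patients, and none says that review continues for them.
- Section 8.3 moves the Day 14 laboratory assessments to the day of withdrawal.
- Section 13.2 follows adverse-event withdrawals for safety. This may end at discharge, when the event resolves or stabilises, or when the PI decides.
- Section 6.6 makes review of records after withdrawal or completion an optional consent item.

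On how withdrawals arise, Section 12.3.1 says of an interruption for toxicity: "Given the short trial duration, this will likely result in participant withdrawal from the study". Section 12.3.2 says that if the event recurs at the reduced dose, "treatment will be held and the subject will be withdrawn from the study". Section 7.1 also allows withdrawal at ICU transfer, with or without advanced support, and by investigator judgement.

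The primary endpoint (Section 4.2) is progression to advanced respiratory support. It has no tolerability component. The 50% control rate in Section 15 refers to the hospitalization.

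**The concern.** An intent-to-treat estimate needs the outcome of every patient over the same risk period, whether or not study drug was stopped. The documents do not separate stopping drug from leaving the study, and what they commit to collect and analyse ends at termination. A patient withdrawn on day 4 for toxicity who needs high-flow oxygen on day 7 has had the event that the endpoint describes, within the period that the planning rate covers. Nothing in the text ensures that this event reaches the analysis.

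The treatment-failure label raises a second question. If it is only a flag, the endpoint is untouched. If an analyst counts it as an event, the endpoint becomes a composite of respiratory failure and intolerance. Neither Section 15 nor the SAP settles this, so two analysts could code the same patient differently.

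The result feeds a decision rule: if the 80% interval excludes zero, the difference is declared clinically meaningful and informs a larger trial. With about 30 patients, a few endpoint classifications matter.

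**Working it through.** **Which withdrawals are exposed.** A patient withdrawn because advanced support was started has already had the event, and the daily record captures it. The gap concerns patients withdrawn before any event who then progress in hospital: after toxicity, by investigator decision, or at ICU transfer without advanced support.

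**Inputs.** Section 15 gives 30 patients at 2:1 (10 placebo, 20 sirolimus), rates of 0.50 and 0.25, and a two-sided 80% interval. Hence z = 1.2816. The plan names no interval method, so the Wald interval is assumed. It gives no withdrawal rate, so every loss rate below is an assumption.

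**The plan's sample size.** The placebo n at which the Wald interval just excludes zero is 1.2816² × (0.25 + 0.1875/2) / 0.25² = 9.03, rounded up to 10. With 20 on sirolimus this gives 30, the plan's figure.

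**Single results.** The interval is d ± 1.2816 × √[p₁(1−p₁)/10 + p₂(1−p₂)/20], with d placebo minus sirolimus. For 5/10 versus 5/20 the standard error is √(0.025 + 0.009375) = 0.1854, so the interval is 0.25 ± 0.2376.

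| Placebo | Sirolimus | What changed | 80% Wald interval (points) |
|---|---|---|---|
| 5/10 | 5/20 | planning result | 1.2 to 48.8 |
| 4/10 | 5/20 | one placebo event missed | −8.4 to 38.4 |
| 5/10 | 6/20 | one sirolimus withdrawal counted as an event | −4.1 to 44.1 |
| 4/10 | 4/20 | one event missed in each arm | −2.9 to 42.9 |
| 5/10 | 4/20 | one sirolimus event missed | 6.7 to 53.3 |

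Newcombe and Miettinen–Nurminen intervals agree in all five rows on whether zero is excluded.

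**Across possible results.** Exact binomial enumeration of all outcomes with 10 and 20 patients gives a 55.5% chance that the lower Wald limit exceeds zero at 0.50 versus 0.25. Two symmetric scenarios follow:
- A share m of events is missed in both arms, so each rate becomes p(1−m).
- A share i of each arm is counted as failing for intolerance, independently of progression, so each rate becomes p + (1−p)i.

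| Assumed share | Missed events, both arms | Intolerance counted as events, both arms |
|---|---|---|
| 0% | 55.5% | 55.5% |
| 5% | 52.8% | 53.0% |
| 10% | 50.0% | 50.4% |
| 20% | 44.3% | 45.4% |

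**One-sided versions show why the direction is unknown.** If 5%, 10% or 20% of non-progressors on sirolimus only were counted as events, the 55.5% would fall to 47.6%, 39.9% or 26.0%. If instead 5%, 10% or 20% of sirolimus events only were missed, with a true rate of 0.50 in both arms, the chance of wrongly favouring sirolimus would rise from 12.4% to 15.2%, 18.5% or 26.0%.

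**The case against.** A reader might infer that Section 13.1.2 excludes data after withdrawal and so contradicts intent-to-treat. It does not. It is an inclusion rule that directly follows a statement of the intent-to-treat approach, and its natural purpose is to keep withdrawn patients in the analysis. Section 13.1.4's promise to seek endpoint evaluations can be read as separate from the evaluations timed at termination. Section 6.6 also provides for record review after withdrawal. What stands against this is that the Section 6.6 permission is optional and is justified by possible long-term effects, and that no section states that endpoint review continues. The gap is narrower than an exclusion, but it is open.

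A reader might also infer that drug-related withdrawals are recoded as primary events. The documents do not say so. The verb used is compatible with a descriptive flag, and the analysis sections never mention treatment failure. The defect is an undefined term.

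Nor does the plan forecast frequent toxicity withdrawals. Section 12.3.1 says what is likely if toxicity forces an interruption, and Section 12.3.2 allows a hold and restart before withdrawal on recurrence.

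Finally, the changes of conclusion from one patient start from the planning result, whose lower limit is only 1.2 points above zero. They largely reflect the sample size. Under equal modest loss in both arms the effect is mild. This is accepted.

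**Conclusion.** The point holds in limited form. The withdrawal rules secure primary-endpoint data only to termination, so a later in-hospital event can be missed despite the intent-to-treat label. The role of the treatment-failure label in the analysis is undefined. It does not follow that later data are barred, that the endpoint has been changed, or that bias favours either arm.

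The size depends on a withdrawal rate that the documents do not give. With equal loss of 5% to 20% of events, the chance of an interval favouring sirolimus falls by about 3 to 11 percentage points (55.5% to between 52.8% and 44.3%). These figures assume the Wald interval, exactly 10 and 20 patients, and true rates of 50% and 25%. Unequal loss could matter more, in either direction. The issue is worth correcting because the remedy is specific and cheap and the endpoint is already read from the inpatient chart.

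**What to change.** Leave the rules on stopping study drug as they are, and separate stopping drug from ending data collection.

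1. State that the existing chart review of advanced respiratory support and vital status continues for withdrawn patients to the end of a stated endpoint window, for example hospital discharge, unless consent for data use is withdrawn. Align the consent form and the optional permission in Section 6.6 with this.
2. Replace the Section 13.1.2 sentence with: *Primary-endpoint data acquired before and after study-drug discontinuation or withdrawal will be included in the primary analysis, as randomised, unless the patient withdraws consent for data use.* This keeps a consent exception.
3. State in Section 13.1.4 and the SAP that the treatment-failure label is not a primary event and is used only descriptively or in a labelled sensitivity analysis.

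The cost is wording changes in the protocol, SAP and consent form, and some extra chart review. No new visits are needed. How to treat patients replaced before their first dose (Sections 13.1.4 and 13.3) is a separate question that this change does not settle.
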